#### OBJECTIVES:

The main objective for this study is to test the MBCT group with women who are currently seeking treatment for low sexual interest/desire and/or arousal and compare it to a support group.

#### RESEARCH METHOD:

Recruitment: Women who are currently seeking treatment at the BC Centre for Sexual Medicine, who have participated in other studies in our laboratory and expressed interest in being contacted for future research, and who see our advertisements in the community (including public transit advertising) will be candidates for this study. Patients from BC Women's Hospital and Health Centre's Complex Chronic Diseases Program who have provided permission to be contacted for future research will be candidates for the study. Those who are seen for an initial assessment by one of the Co-Investigators, or any of the clinicians at the BC Centre for Sexual Medicine will be informed about the study at the conclusion of their assessment if they are determined to meet inclusion criteria. After briefly mentioning the study, the clinician will give interested women a handout (one-page information sheet) that briefly outlines the methods of the study and the criteria for inclusion, as well as contact information for the study coordinator. A copy of the consent form will be included with the handout to allow the woman to review the consent prior to contacting the study coordinator about the study. Specific instructions will be included informing women that the consent form provided at this time is for information purposes and should not be returned until the woman has spoken to the study coordinator. For women in our database of former participants, the study coordinator of the study in which they participated will contact them by phone or email, inform them about the study, and email them the handout with instructions to contact the study coordinator if they are interested in participating. For women in the "permission to be contacted for research" database from the Complex Chronic Disease program at BC Women's Hospital, they will be contacted by the coordinator from the program and interested women can contact the DESIRE study coordinator. Interested candidates from the community will contact the study coordinator directly. She will perform a detailed telephone screen for all potential participants that further assesses study eligibility and explains the methods in more detail, and then mail/email a copy of the consent form to participants. If, after reading the consent form, the woman is interested in taking part, she will contact the Study Coordinator to set up an in-person meeting with a trained graduate student in clinical or counselling psychology at UBC who will carry out the in-person assessments under the supervision of the PI. At this time, her eligibility will be confirmed and she will sign the

consent form. Following enrolment, she will be randomized to either group mindfulness-based therapy or support group therapy and will be registered for the next study group. Arrangements will also be made to complete the saliva sampling, pre-treatment questionnaires, and the sexual psychophysiological assessment.

Inclusion criteria for treatment group includes: any woman between the ages of 19-65, fluent in English, and who experiences distressing sexual interest/desire and or sexual arousal concerns. Exclusion criteria include: a psychiatric or medical condition precluding group attendance or homework completion, and Borderline Personality Disorder (for which mindfulness meditation may cause dissociation and is therefore counter-indicated; Sachse, Keville, & Feigenbaum, 2011).

Procedures: Participants will be randomly assigned to either the MBCT group or the support group (control condition). The purpose of the support group is to control for any effect of the sexuality education, discussion, and support provided in the MBCT group.

All participants will meet in-person with a trained graduate student in clinical or counselling psychology to ask any further questions about the study, to review study protocol, and discuss participant remuneration- \$55/assessment (\$25 per questionnaire package plus \$30/ per laboratory-based assessment and at-home saliva sample collection) for each of the four times completed. Participants will receive their saliva sampling kit (which includes all necessary sampling equipment) and detailed written and verbal instructions on how to collect their samples.

After saliva samples have been collected, participants will return their saliva sampling kits to the Study Coordinator when they take part in an individual sexual psychophysiological assessment in the PI's laboratory (UBC Sexual Health Lab) located in the Diamond Health Care Centre at Vancouver Hospital. Women will be asked to undergo a heartbeat perception task and a sexual arousal assessment.

The Heartbeat Perception task, performed according to the Mental Tracking Method proposed by Schandry (1981), involves the silent counting of perceived heartbeats during four intervals of varying duration (25, 35, 45, and 55 seconds) separated by a 30 second resting period. After each counting period participants will be asked to report the number of counted heartbeats. Electrocardiogram measurements will be taken to determine actual heart rate. Participants will wear non-polarized Ag-AgCl electrodes attached to two points on the body (mid right clavicle and lower left ribcage). Signals will be recorded and analyzed by a computer-based data acquisition system (MP150; Biopac Systems, Inc.) The Heartbeat Perception task is a well-validated measure of the ability to detect changes within the body known as Interoceptive Awareness (Dunn et al., 2007; Jones, 1994; Wildmann & Jones, 1982).

The sexual arousal assessment will involve exposure to brief audiovisual films which include erotic content. While viewing the film, a woman's vaginal pulse amplitude (VPA) will be measured with a Vaginal Photoplethysmograph which has been found to be a sensitive and specific measure of genital arousal (Laan & Everaerd, 1995). Participants will indicate their levels of subjective arousal while viewing the film by using a device manufactured for the UBC Sexual Health Lab called the "arousometer"- a computer mouse mounted on a metal track divided into 10 equally spaced intervals corresponding to "sexually turned off" (-2) to "the most sexually aroused you have ever been or could imagine being" (7). This device allows continuous self-report measurement of subjective sexual arousal while viewing the erotic films. Immediately before and after watching the films, participants will complete a pre and post film questionnaire that assess mood and reactions to the erotic film (Heiman & Rowland, 1983). This assessment is performed pre-treatment, 2-4 weeks post treatment and 6 and 12 months post treatment. Women who enroll in the study and complete their pre-treatment physiological assessment more than 2.5 months before their group starts will undergo an additional sexual arousal assessment

prior to the group. Each woman will be provided with an individualized link to online questionnaires to be completed before their assessments.

Each group will have between 6-8 women and we hope to run approximately four groups per year. The group will be led by the PI, the Co-Investigator ([name]), and/or the team of trained clinicians at the BC Centre for Sexual Medicine who have been involved in designing and carrying out similar groups over the past six years. Groups will have at least 2 facilitators. All groups will take place in a private group room at the Diamond Health Care Centre, located at Vancouver General Hospital, at [name].

The 8-session MBCT group is based on a variety of empirically supported techniques, and integrates elements of education, mindfulness skills, and sex therapy. It consists of eight, two-hour long sessions spaced one week apart. Each woman will participate for 16 hours of group time. In addition, participants are also given handouts and asked to complete approximately 10-60 minutes/day of at-home practice/skills, which may include reading material, mindfulness exercises, and behavioural exercises between sessions. The treatment in the MBCT group is very similar to that of the 4-session PED previously tested and found effective in our centre; participants who receive the expanded version will, however, be given more time to practice the various exercises (e.g., mindfulness exercises) in session, and more time will be devoted to inquiry about participants' in-session practice experiences. The support group will include all of the same material except for the mindfulness practice in session and at home. Approximately 10% of the group sessions will be audio-recorded to ensure facilitator adherence to the treatment manual.

Participants will complete brief questionnaires online and over the telephone between sessions 4 and 5 of their therapy group, in order to establish the temporal sequence of changes in the main outcome variable and hypothesized mediators.

After the conclusion of group session 8, women will be provided with an individualized link to online questionnaires, which will be nearly identical to those completed prior to their first assessment, and a second saliva sampling kit. In addition, women will repeat their sexual psychophysiological assessment at the UBC Sexual Health Lab. Women will also be asked about their experience with the mindfulness practices and/or sexuality worksheets at each post-treatment assessment. Questionnaires, at-home saliva sample collection, and the in-lab psychophysiological assessments will also be done 6 and 12 months after completing the 8-session group treatment. All online questionnaires for women in both treatment groups will be administered with SurveyMonkey™.

Participants who have completed the study will be invited to take part as a "patient partner," which will involve attending a focus group meeting with the study investigators to provide insight and feedback on their experience living with Sexual Interest/Arousal Disorder, as well as get their feedback on what they would find most interesting and relevant to viewers regarding the findings of another study called MODEST (Mood, Stress, and Sexual Desire in Women, CREB number = H10-02067), which also examined women's low sexual desire. This will help to develop a script to create a knowledge translation infographic video in the future. This meeting would take approximately 2 hours and patient partners would receive \$50 for their time and cost of parking. This is not a required study procedure but rather an invitation if former participants would like to share their experience. The meeting will be a single 2 hour session with up to three women with low desire, two facilitators, and a note-taker from the study team. The entire session will be audio-recorded and later transcribed. No individual names will be used in the transcript. Patient Partners will be asked to respect the confidentiality of those who attend this focus group meeting, and will be told that facilitators cannot control what other participants do with the information discussed, so that they can make an informed decision about whether or not to participate in the focus group.

Specification of Endpoints: The primary endpoint in this study will be sexual distress given that distress associated with impaired sexual functioning is the reason that women provide for

seeking treatment. Sexual distress will be measured with the revised version of the Female Sexual Distress Scale-R (Derogatis et al., 2008). Measurement of sexual interest/desire, arousal (both self-report and psychophysiological), stress hormone ratios, and Interoceptive Awareness represent secondary endpoints. Psychophysiological sexual arousal will be measured with a vaginal photoplethysmograph in the UBC Sexual Health Laboratory. Stress hormone ratios will be measured through calculating the cortisol:DHEA slope within participants' saliva samples. This will be done by measuring the change in cortisol:DHEA secretions over the course of the day, and calculating a simple difference score (PM minus AM values). Interoceptive Awareness will be measured using the Heartbeat Perception task (Schandry, 1981) at the time of the sexual arousal assessment and with the Multidimensional Assessment of Interoceptive Awareness (MAIA; Mehling et al., 2012) questionnaire. Self-reported sexual desire and arousal will be assessed with the Female Sexual Function Inventory (FSFI; Rosen et al., 2000), the Sexual Pleasure Questionnaire (a two-question supplement to the FSFI developed for this study), and the Sexual Interest and Desire Inventory (SIDI; Clayton et al. 2006). Other endpoints include: relationship satisfaction, which will be measured with the Relationship Assessment Scale (Hendrick, 1988); motivations for sex, which will be measured with the Motivations for Sex Measure (Muise et al., 2013); disruptions to the sexual response cycle, which will be measured using the Sexual Response Cycle Worksheet (Basson, 2000); perceived stress, which will be measured with the Perceived Stress Scale (Cohen, Kamarck, & Mermelstein, 1983); depression, which will be measured with the Beck Depression Inventory-II (BDI-II; Beck, Steer, & Brown, 1996) or the Hamilton Depression Scale - Short Form (McIntyre et al., 2005); rumination, which will be measured with the Ruminative Responses Scale (Treynor, Gonzalez, & Nolen-Hoeksema, 2003) or the Rumination-Reflection Questionnaire - Adapted Rumination Subscale (adapted from Trapnell & Campbell, 1999 to inquire about sexuality-related rumination); trait anxiety and situational anxiety at the sexual arousal assessments, which will be measured with the State-Trait Anxiety Inventory (Spielberger, Gorsuch, & Lushene, 1970); and anxiety sensitivity, which will be measured with the Anxiety Sensitivity Index - 3 (Taylor et al., 2007). Mindfulness, self-compassion, and non-attachment will be measured with the Five Factor Mindfulness questionnaire (Baer, Smith, Hopkins, Krietemeyer & Tony, 2006), Self-Compassion Scale (Neff, 2003), and Non-Attachment Scale (Sahdra, Shaver, & Brown, 2010), respectively. We will assess socially desirable responding (impression management and self-deceptive enhancement) with the Balanced Inventory of Desirable Responding-6 (BIDR-6; Paulhus, 1998), expectations of change with treatment with the Expectations Measure [a two-item questionnaire completed following the session 1, designed for and used in our approved mindfulness-based treatment study for provoked vestibulodynia (H12-02358)], and participants' impressions of change with treatment with the Patient Global Impression of Change Scale - Revised (adapted from Hurst & Bolton, 2004; as used in H12-02358).

**Measures:** Questionnaires to be included in this study will be administered to women online. Women choosing to have a hard copy of the questionnaire will be provided with such questionnaires at the time of their in-person sexual arousal assessment. The following instruments will be used at all testing times: (1) Beck Depression Inventory-II (Beck et al., 1996) or the Hamilton Depression Scale - Short Form (McIntyre et al., 2005); (2) Female Sexual Distress Scale-Revised (Derogatis et al., 2008); (3) Female Sexual Function Index (Rosen et al., 2000); (4) Five Facet Mindfulness Questionnaire (Baer et al., 2006); (5) Sexual Interest and Desire Inventory (Clayton et al., 2006); (6) State-Trait Anxiety Inventory - State Form (Spielberger et al., 1970); (7) Sexual Pleasure Questionnaire; (8) Multidimensional Assessment of Interoceptive Awareness (Mehling et al., 2012); (9) Ruminative Responses Scale (Treynor et al., 2003) or Rumination-Reflection Questionnaire - Adapted Rumination Subscale (adapted from Trapnell & Campbell, 1999); (10) Anxiety Sensitivity Index - 3 (Taylor et al., 2007); (11) Self-Compassion Scale (Neff, 2003); (12) Non-Attachment Scale (Sahdra, Shaver, & Brown, 2010); (13) Perceived Stress Scale (Cohen, Kamarck, & Mermelstein, 1983); (14) Relationship

Assessment Scale (Hendrick, 1988); (15) Film Scale Before and After -1983 (Heiman & Rowland, 1983).

The following questionnaires will be used at baseline only: (16) Balanced Inventory of Desirable Responding-6 (Paulhus, 1998); (17) State-Trait Anxiety Inventory - Trait Form (Spielberger et al., 1970); and (18) Expectations Measure (following session 1).

The following questionnaires will be used at post-treatment (approximately 4-6 weeks after session 8), and at 6- and 12-month follow-ups only: (19) Patient Global Impression of Change Scale - Revised (adapted from Hurst & Bolton, 2004). For post-treatment assessments only, participants will complete an investigator-derived MIND or STEP Follow-Up Form in order to assess completion of group homework, which will be administered by a trained research assistant at each assessment point.

All questionnaires for the study will be completed online using Survey Monkey, except for the Hamilton Depression Scale - Short Form, which will be administered by a trained research assistant at each assessment point. Women who prefer to receive a hard copy of the questionnaires will be sent the questionnaire package via mail.

At baseline, participants will complete an investigator-derived Dysmenorrhea Questionnaire in order to assess painful menstruation. This questionnaire is being used in the COMFORT study (H12-02358) with women with provoked vestibulodynia, as dysmenorrhea has been linked to the development of chronic pain conditions. When the COMFORT study's data are analyzed, rates of dysmenorrhea in the two different studies will be compared.

The following questionnaires will be used at pre-treatment and post treatment (approximately 4-6 weeks after session 8) only: (20) Pelvic Floor Distress Inventory - short form 20 (Barber, Walters, & Bump, 2005); (21) Pelvic Floor Impact Questionnaire - short form 7 (Barber, Walters, & Bump, 2005).

For the control group, data collected from the VENUS study will be used in the DESIRE Study from participants who consent to participating. Demographic information and the following validated measures will be analyzed from the VENUS Study: (1) Female Sexual Interest and Desire Inventory (SIDI-F; Clayton et al, 2006); (2) Female Sexual Distress Scale (Derogatis, Rosen, Leiblum, Burnett, & Heiman, 2002).

For control group participants recruited from the community, demographic information and the following validated measures will be analyzed: (1) Female Sexual Interest and Desire Inventory (SIDI-F; Clayton et al, 2006); (2) Female Sexual Distress Scale (Derogatis, Rosen, Leiblum, Burnett, & Heiman, 2002).

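### Women are randomised and registered for a group with the baseline questionnaires still to be completed, and nothing withholds the arm until the primary endpoint has been answered

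*Combined protocol and SAP*

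**What the plan says.** The Recruitment text under RESEARCH METHOD gives the sequence. At an in-person meeting eligibility is confirmed and consent is signed. Then: "Following enrolment, she will be randomized to either group mindfulness-based therapy or support group therapy and will be registered for the next study group". The sentence after it reads: "Arrangements will also be made to complete the saliva sampling, pre-treatment questionnaires, and the sexual psychophysiological assessment". The Procedures text adds: "Each woman will be provided with an individualized link to online questionnaires to be completed before their assessments". It ties that link to the assessment visit, not to the moment a woman learns her arm.

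Under Specification of Endpoints, "The primary endpoint in this study will be sexual distress", measured with the FSDS-R. The Measures section lists the FSDS-R among the instruments used at every testing time, so its baseline belongs to the pre-treatment package. On the contrast between arms, Procedures states: "The support group will include all of the same material except for the mindfulness practice in session and at home".

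Hypothesis 3 predicts larger changes in the MBCT arm. Data analyses tests the outcomes with a repeated measures ANOVA, with arm between subjects and five levels of time: waitlist, pre-group, post-group and two follow-ups.

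**The concern.** Allocation and a place in a particular group are settled while the baseline of a self-reported primary endpoint is still outstanding. A woman who knows she is going to the mindfulness arm, or to the support arm, might rate her distress differently from one who does not yet know. If that reaction differs between arms, the baselines differ for a reason other than chance.

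The planned test looks at change, and the pre-group score is one of its time levels, so such a difference would feed directly into the comparison that hypothesis 3 rests on. Later visits cannot be masked for the women, who know whether they were taught mindfulness. Baseline is the one measurement that can be fully protected.

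**Working it through.** The plan gives no figure on this point, so there is none to reproduce. The check is a reading of the sequence, followed by an illustration.

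**Sequence**

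1. Consent and eligibility come first, then randomisation and group registration (Recruitment).
2. At that point the pre-treatment questionnaires are being arranged, not reported as done. The wording does not strictly fix whether a given woman completes them before or after assignment.
3. No available section says when she is told her arm, or that it is held back. Title and consent pages were removed from the copy reviewed and are not counted as silent.
4. The wait can be long. Women who "complete their pre-treatment physiological assessment more than 2.5 months before their group starts will undergo an additional sexual arousal assessment". Only the arousal assessment is expressly repeated.

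The plan therefore permits an FSDS-R baseline answered with the arm known, but does not state that it happens.

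**Effect on the contrast**

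Let one arm's pre-group mean shift by *b*, with a fraction *p* of the shift persisting later. The between-arm difference in change from pre-group moves by (1 − p)·b in size: all of *b* if nothing persists, b/2 if half does, zero if all does.

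**Illustration**

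Every input here is assumed; the documents give no sample size, SD, correlation or shift. Assume no true effect, compound symmetry, alpha 0.05, n = 60 per arm, ρ = 0.5 and a shift of s = 0.20 SD in one arm. For a shift pattern x over T time levels,

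ncp = n · (s²/2) · Σ(x_t − x̄)² / (1 − ρ), with df = T − 1 and (T − 1)(2n − 2).

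The multiplier is 60 × 0.02 / 0.5 = 2.4.

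Data analyses lists five levels. Procedures pays women "for each of the four times completed", so four levels are shown as well.

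| Levels (order: waitlist if present, pre, post, 6 m, 12 m) | Pattern x | Σ(x_t − x̄)² | ncp | Rejection |
|---|---|---|---|---|
| Five, waitlist also shifted, none persists | 1,1,0,0,0 | 2 − 4/5 = 1.2 | 2.88 | 0.233 |
| Five, waitlist not shifted, none persists | 0,1,0,0,0 | 1 − 1/5 = 0.8 | 1.92 | 0.165 |
| Five, waitlist not shifted, all persists | 0,1,1,1,1 | 4 − 16/5 = 0.8 | 1.92 | 0.165 |
| Four, none persists | 1,0,0,0 | 0.75 | 1.80 | 0.175 |
| Four, half persists | 1,½,½,½ | 0.1875 | 0.45 | 0.078 |
| Four, all persists | 1,1,1,1 | 0 | 0 | 0.05 |

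The third row shows that, with an unshifted waitlist level, the omnibus test can reject even when the shift persists fully and change from pre-group is unbiased.

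The range over 30 to 100 women per arm and ρ from 0.3 to 0.7, with none persisting, is:

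- **Four levels:** 0.059 to 0.133 for a 0.10 SD shift, and 0.090 to 0.438 for 0.20 SD.
- **Five levels, across both waitlist cases:** 0.058 to 0.171 for 0.10 SD, and 0.086 to 0.602 for 0.20 SD.

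With no shift the rate is 0.05.

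**The case against.** The strongest reply is that this rests on silence. The order is not strictly fixed, early disclosure is an inference from group registration, and a consent form and information sheet exist that may say when women learn their arm. That stands, and it limits the point to what the plan permits. A reader might infer that the baseline was unblinded or is biased; the documents support neither.

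A second reply is that the design makes a differential shift less likely. The comparator is an active group sharing all but the mindfulness practice, socially desirable responding is measured at baseline and may be adjusted for, and expectations are measured and tested as a moderator. This is fair as to plausibility. None of it conceals the arm, however, and expectations are recorded only after session 1, too late to show whether they differed when baseline was answered.

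A reader might also infer that an unmasked assessor affects the primary endpoint, because the meeting is with "a trained graduate student in clinical or counselling psychology at UBC who will carry out the in-person assessments under the supervision of the PI". That does not follow: women complete the FSDS-R themselves, online or on paper. Assessor knowledge is at most a separate matter for other measures.

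Finally, the rejection rates depend on the number of time levels and on every assumed input. This is correct; they show scale only and are not evidence of bias.

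**Conclusion.** The point holds as a gap in the stated sequence. Randomisation and registration come straight after consent, baseline is still to be completed, and no available text keeps the arm from the woman until it is. The primary endpoint's baseline is therefore unprotected against a reaction to allocation. The possible bias in the between-arm difference in change equals the non-persisting part of any differential shift.

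The size of that shift is unknown and may be zero. Under the assumed inputs above (60 per arm, ρ = 0.5, 0.20 SD, none persisting), the five-level test would reject with probability 0.165 to 0.233 in place of 0.05. The change is worth making because it closes this route whatever the size of the shift, and it costs little.

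**What to change.** In the Recruitment text under RESEARCH METHOD, where randomisation is described, state that each woman completes the pre-treatment questionnaires, the saliva kit and the first laboratory assessment before her allocation is disclosed to her. Either of two routes achieves this: randomise after baseline is complete, or reserve a place on a group without naming the arm.

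In Procedures, label any additional arousal assessment taken after disclosure as post-allocation. Leave the waitlist and pre-group levels in Data analyses as they are. Declaring the first scores to be the baseline for hypothesis 3 would go too far, since it could replace a pre-group arousal value with an older one.

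The cost is one sentence and one label, with no new visit or instrument. Women learn their arm later, and the coordinator must hold group details back until baseline is in. If this is already the practice, only the wording changes.

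### The plan describes no question, worded alike in both arms, on unwanted effects or on stopping because of one, and no count by arm; two items on existing contacts would supply this

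*Combined protocol and SAP*

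**What the plan says.** All references are to the combined protocol and SAP.

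- **Difference between arms** (RESEARCH METHOD, Procedures): "The support group will include all of the same material except for the mindfulness practice in session and at home".
- **Experience question** (Procedures): "Women will also be asked about their experience with the mindfulness practices and/or sexuality worksheets at each post-treatment assessment". No wording is given.
- **Homework form** (Measures): at post-treatment assessments "participants will complete an investigator-derived MIND or STEP Follow-Up Form in order to assess completion of group homework". The form has two named versions, and its content is not shown.
- **Scales common to both arms** (Measures): "The following instruments will be used at all testing times" introduces a list that includes depression, state anxiety and perceived stress. A global rating of change is added at post-treatment "and at 6- and 12-month follow-ups only: (19) Patient Global Impression of Change Scale - Revised".
- **In-session inquiry** (Procedures, description of MBCT): "more time will be devoted to inquiry about participants", the subject being their practice experiences in session.
- **Audio-recording** (Procedures): about 10% of group sessions, to check that facilitators follow the manual.
- **Contact during treatment** (Procedures): brief online and telephone questionnaires "between sessions 4 and 5 of their therapy group, in order to establish the temporal sequence of changes in the main outcome variable" and the hypothesised mediators.
- **Dissociation** (exclusion criteria): named once, as the reason for excluding women with Borderline Personality Disorder.
- **Data analyses**: repeated measures ANOVA, regression, mediation, moderation and qualitative work. Unwanted effects and reasons for stopping are not mentioned.

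**The concern.** A trial that isolates one active ingredient should be able to say how many women in each arm had an unwanted effect, and how many gave up home exercises or sessions because of one. That needs the same question in both arms. If problems surface mainly through conversation about practice in the MBCT sessions, they are more likely to be noticed in that arm than in the other.

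Homework completion does not close the gap. As described, it shows that practice stopped but not why. The reason also matters for interpretation, because Data analyses intends to try to control for degree of homework completion.

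What is at stake is the quality of safety reporting and the chance for a clinician to hear of a problem during treatment. The efficacy estimate is not at stake.

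**Working it through.** **Step 1. Does any described element ask the question?** The document states no sample size, power or event rate, so there is no planned figure to reproduce. The check is a side-by-side reading.

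| Element | Same in both arms? | Stated to ask about unwanted effects? | Stated to ask why a woman stopped? |
|---|---|---|---|
| Experience question | Refers to arm-specific content | No; wording not public | No; wording not public |
| MIND or STEP form | Two named versions | No; purpose is homework completion | No |
| Common symptom scales | Yes | No; they measure symptom level | No |
| Global impression of change | Yes | No; it measures overall change | No |
| In-session inquiry | Described for MBCT | Not stated | Not stated |
| Audio-recording of about 10% of sessions | Not limited to one arm | No; purpose is facilitator adherence | No |
| Contact between sessions 4 and 5 | Not limited to one arm | No; purpose is the timing of change | No |

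No row meets all three conditions, and Data analyses lists no count by arm.

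**Step 2. Could the existing contacts carry the items?** There are four: between sessions 4 and 5, post-treatment, 6 months and 12 months. Two items at each add at most 2 × 4 = 8 answers per woman. Both arms use the same online survey platform, so identical wording is practical.

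**Step 3. What could the counts show? (Illustration only.)** Procedures gives 6-8 women per group and about four groups a year. Assume that this covers both arms, that allocation is equal, and that accrual lasts 2-4 years.

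- Per year: 4 × 6 = 24 to 4 × 8 = 32 women, so 12-16 per arm.
- Per arm: 12 × 2 = 24 to 16 × 4 = 64.

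Assume also a true rate p of 2-10% in one arm; the documents give no basis for this range. Expected count = n × p. Chance of at least one report = 1 − (1 − p)^n. One-sided 95% upper limit after zero reports = 1 − 0.05^(1/n). If 20% are not reached (assumed), n falls to 0.8 × 24 ≈ 19 or 0.8 × 64 ≈ 51.

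| Women asked per arm | Expected count, 2% to 10% | Chance of at least one, 2% to 10% | Upper limit after zero |
|---|---|---|---|
| 24 | 0.5 to 2.4 | 38% to 92% | 11.7% |
| 19 | 0.4 to 1.9 | 32% to 86% | 14.6% |
| 64 | 1.3 to 6.4 | 73% to 99.9% | 4.6% |
| 51 | 1.0 to 5.1 | 64% to 99.5% | 5.7% |

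Power to separate 10% from 2% (two-sided 5%) is 21% with 24 per arm and 48% with 64 per arm by the pooled normal approximation. With Fisher's exact test it is 5.5% and 31%. A between-arm test would therefore be uninformative, and the counts should be descriptive.

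**The case against.** The strongest reply is that the absence rests on wording no outside reader can see. The experience question and the follow-up forms are where unwanted effects and reasons for stopping would naturally come up, and the treatment manual and consent pages are not available either. This stands, and it limits the claim to what the public text describes. A reader might infer that the trial collected no information on harm; the documents do not support that.

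A second reply is that the risk premise is thin. That also stands. Dissociation is named only for a group that is excluded. A reader might infer that the protocol concedes a risk in enrolled women, but it does not, so dissociation belongs in the item only as one example.

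Third, the information is not lost for good. Women meet at least two facilitators over eight sessions and are seen again up to 12 months, so many could be asked later. This stands too: for women still in contact, the cost is incomplete and less accurate recall. Early leavers are the harder case, and added items may miss them as well.

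Fourth, identical wording does not guarantee identical meaning. Home exercises differ by arm, and women know which treatment they receive, so prompting may differ. This is a reason to read the counts with care. It is not a reason to leave the question out.

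**Conclusion.** The concern holds in limited form. The public text describes no commonly worded question on unwanted effects or on stopping because of one, and no count by arm. As described, that information would come only from later recall or unstructured contact with facilitators. The unseen forms may already supply part of it.

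A reader might go further and infer that the treatment comparison is biased or its error rate altered. Nothing in the documents supports that: the primary endpoint, sexual distress, and its analysis do not depend on these items.

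The size cannot be stated from the documents. The illustrative figures rest wholly on assumed accrual, allocation, event rate and reach. They show only that counts would be small and could not settle whether an effect is more frequent with MBCT. The priority is modest and confidence is medium, because the wording of the forms is not public.

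**What to change.** Add two items in both arms, in identical words that do not mention mindfulness:

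1. whether the woman has had any unwanted effect, with dissociation given as one example;
2. whether she stopped home exercises or sessions because of one.

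Ask them at the existing contact between sessions 4 and 5 and at the post-treatment, 6-month and 12-month assessments. Try to reach women who have stopped attending where possible; the protocol does not say whether they are still contacted. Pass positive answers to the existing study clinicians. In Data analyses, add a line stating that counts will be reported by randomised arm, with the number asked as denominator and no significance test.

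If the MIND or STEP form or the experience question already contains such items in the same words for both arms, it is enough to say so, extend them to the contact between sessions 4 and 5, and add the count by arm.

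The cost is a short amendment, a few minutes per woman, a route for handling positive answers, and one descriptive table. No visit is added and no efficacy analysis changes. The drawbacks are some prompting of symptom reports, possibly unequal between arms, and early leavers who may still be missed; the denominator will show how many women were not asked.
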